#### 9.3.1 PRIMARY OUTCOME MEASURE ANALYSIS

Primary outcome measures of POSAS scores at 1 week, 1 month, and 6months post-operatively will be analyzed using descriptive statistics, including n, mean, standard deviation, median, minimum, maximum, and skewness.

#### 9.3.2 SECONDARY OUTCOME MEASURE ANALYSIS

Secondary outcome measures of pain medication use, overall satisfaction (scale 1 to 10), days to return to work, days of occupational therapy, complication rate, and recurrence rate will be analyzed using descriptive statistics, including n, mean, standard deviation, median, minimum, maximum, and skewness.

#### 9.3.3 EXPLORATORY MEASURES ANALYSIS

All exploratory variables will be summarized with descriptive statistics appropriate to the scale of measurement for each variable.

#### 9.3.4 SAFETY ANALYSIS

Safety analyses will include the incidence and severity of adverse events observed over the study assessment period. These will be tabulated and presented overall and by relatedness, severity, and preferred term.

### 9.4 SUBGROUP ANALYSIS

Subgroup analyses will be performed to explore their relationship to key study outcomes.

## 9.5 EXPLORATORY ANALYSES

POSAS scores at 1 week, 1 month, and 6 months post-operatively will be analyzed between patients treated with endoscopic versus open release using 2-sample t-tests. Differences in pain medication use, days before return to work, duration of OT, operative time, overall satisfaction, complication and recurrence rates between patients treated with endoscopic versus open surgical release of the A1 pulley will be tested for significance using 2-sample t-tests. Additional analyses of possible relationships between outcomes may also be performed using appropriate inferential tests.

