## 7 STUDY INTERVENTION DISCONTINUATION AND PARTICIPANT DISCONTINUATION/WITHDRAWAL

### 7.1 EARLY DISCONTINUATION OF SUBJECTS

Each subject reserves the right to withdraw from the study at any time without jeopardy to their future medical care. All follow-up assessments and procedures should be performed at the final study visit. For any subject who discontinues from the study, the date and reason for discontinuation will be recorded.

If a subject fails to return for one or more scheduled study visits, the Investigator will attempt to contact the subject to determine and document the reason the subject has failed to return and to encourage compliance with the study visit schedule.

A subject may be discontinued from the study for the following reasons:

- Subject did not undergo surgical treatment as it was deemed not warranted by the Investigator
- Since enrollment in the study, subject has had alternative treatment that would otherwise affect the study questionnaire/outcomes data
- Subject does not complete scheduled follow-up visits per protocol
- Subject has died

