## 9 STATISTICAL PROCEDURES

Every attempt will be made to collect complete data and limit the occurrence of missing data. Due to the descriptive nature of all analyses, no imputation of missing data will be performed. Descriptive summaries will be based on all observations available within each of the relevant analysis populations.

Descriptive statistics will be presented for key outcome measures.

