### 9.1 POPULATIONS FOR ANALYSES

All subjects will be included in the full analysis population. The per protocol population is defined as subjects who have not had any major protocol deviations throughout the study (Section 9.8) and will be analyzed as the primary study group. Other subgroups may be analyzed as detailed in the subgroup analyses section. Subjects that have been discontinued will be excluded from data analysis.

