## 9.6 SAMPLE SIZE CALCULATION

Total POSAS scores range from 12 to 120. Though the POSAS has not been used to assess scarring after trigger finger release, the tool is validated with high internal consistency and reliability.

The trial will be powered to detect a difference in POSAS score of 10, deemed to be clinically significant by the investigators. The POSAS standard deviations in studies previously published on carpal tunnel release and carotid endarterectomies ranges from 1.0 to 11.0. To detect a mean difference in POSAS score of 10 points (SD = 8) with a two-sided significance level of 5% and power of 80% with equal allocation to two arms would require 12 patients in each arm of the trial. Additional subjects may be enrolled, as needed to achieve 12 patients in each treatment arm, in the event of patient death or withdrawal from the study.

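### Separate POSAS t-tests at each visit leave earlier scores out of the 6-month comparison, which can then be biased in either direction if attendance depends on the scar

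*Combined protocol and SAP*

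**What the plan says.** POSAS at 1 week, 1 month and 6 months is the primary outcome (Sections 8.1.1 and 9.2.1). Its primary analysis is a summary only: the scores "will be analyzed using descriptive statistics, including n, mean, standard deviation, median, minimum, maximum, and skewness" (Section 9.3.1). The between-arm comparison is in Section 9.5, where the scores at the three visits "will be analyzed between patients treated with endoscopic versus open release using 2-sample t-tests". No model links the visits, and no missing-data sensitivity analysis is planned.

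On missing data, Section 9 states: "Due to the descriptive nature of all analyses, no imputation of missing data will be performed". It adds: "Descriptive summaries will be based on all observations available within each of the relevant analysis populations".

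Two other rules decide whose scores are available. Section 9.1 makes the per protocol population the one that "will be analyzed as the primary study group", and then says: "Subjects that have been discontinued will be excluded from data analysis". Section 7.1 lists among the permitted reasons for discontinuation: "Subject does not complete scheduled follow-up visits per protocol".

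Section 9.6 says: "The trial will be powered to detect a difference in POSAS score of 10". It assumes SD 8, two-sided 5% and 80% power, and arrives at 12 patients per arm.

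**The concern.** Each patient can give three correlated POSAS scores. A t-test at 6 months sees only the patients scored at 6 months. It estimates the arm difference without bias only if, within each arm, being scored has nothing to do with the scar, or if any selection shifts both arms equally. A model that also uses the earlier scores needs less: attendance may depend on scores already observed.

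Missing 6-month scores are foreseeable. Study visits coincide with routine clinic visits (Section 4.3), Section 7.1 provides for patients who fail to return, and Section 6.2 lets patients skip POSAS questions. Section 9.6 states no attrition rate, and replacement covers death or withdrawal, not a missed visit as such.

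At stake is the 6-month estimate in a trial of 24 patients, where a few selectively absent patients can move an arm mean by one or two points.

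**Working it through.** **1. The plan's own figure.** Inputs from Section 9.6: difference 10, SD 8, two-sided 5%, power 80%, 1:1.

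- Normal approximation: n = 2 × (1.960 + 0.842)² × 8² / 10² = 10.05, so 11 per arm.
- Exact (noncentral t): power 79.6% at 11 per arm and 83.3% at 12.

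The stated 12 per arm is reproduced. With 9 or 8 patients per arm scored at 6 months, exact power falls to 70.2% or 64.3%.

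**2. Information lost when missingness is random.** Let n patients per arm have a 1-month score, n_obs of them a 6-month score, and ρ be the correlation between the two. Relative to the mean of the n_obs observed scores, the variance of the likelihood estimate of the 6-month arm mean is

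ratio = (1 − ρ²) + ρ² × n_obs / n.

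Assume 25% missing (n_obs = 9, n = 12):

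| ρ | Calculation | Ratio | Variance saved |
|---|---|---|---|
| 0.3 | 0.91 + 0.09 × 0.75 | 0.978 | about 2% |
| 0.5 | 0.75 + 0.25 × 0.75 | 0.938 | about 6% |
| 0.7 | 0.51 + 0.49 × 0.75 | 0.878 | about 12% |

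Allowing for small-sample estimation of the slope, roughly 0 to 13% is a fair range. With complete data the saving is nil.

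**3. Bias when attendance depends on the 1-month score.** Lower POSAS is taken as a better scar, and differences are open minus endoscopic, so a positive bias flatters endoscopic release. With equal SDs, the 6-month mean of the attenders is displaced by ρ times the displacement of their 1-month mean.

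As a simple case, suppose the three open-arm patients with the best 1-month scores all miss 6 months and nobody else does. The remaining nine have a 1-month mean about 3.16 points too high, so the 6-month bias is 3.16ρ. That is 0.95, 1.58 and 2.21 points at ρ = 0.3, 0.5 and 0.7. Simulation of 30,000 trials gives 0.94, 1.58 and 2.25, with type I error of the 6-month t-test about 6%, 8% and 10%.

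**4. Three graded mechanisms.** Simulation assumptions: 12 per arm, SD 8, true difference 10, log-odds of missing 6 months rising by 1.5 per SD of better 1-month score, about 31% missing (3.7 of 12) in the affected group.

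| Who skips 6 months | t-test bias, ρ = 0.5 | t-test bias, ρ = 0.7 |
|---|---|---|
| Open-arm patients with better scores only | about +1.3 | about +1.9 |
| Both arms, one rule on the absolute score | about −1.1 | about −1.6 |
| Both arms, same selection within each arm | about 0 | about 0 |

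In the second row more endoscopic patients skip, because the assumed effect gives them better scores. Halving the log-odds slope in the first row gives about +0.9 and +1.2. An estimator that regresses the 6-month score on the 1-month score, standing in for the full likelihood model, stays within about 0.15 points of the truth under all three mechanisms.

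**5. The exclusion rule.** If the three open-arm patients in step 3 are discontinued under Section 7.1 and dropped under Section 9.1, their 1-month scores go too. The 1-month comparison is then itself displaced by about 3.2 points, and no model can recover scores that have been removed.

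**The case against.** The strongest reply is that the t-tests are labelled exploratory, the primary analysis is descriptive, and the synopsis says 24 patients suffice for descriptive summaries and exploratory analyses. Nothing in the documents says that patients with good scars stay away. Section 6.1.3 requires attendance, and Section 7.1 has the investigator contact patients who do not return. If missingness is random or alike in the two arms, the t-test is unbiased and the gain in precision is small.

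Most of this stands, and it limits the point to a conditional one. The exploratory label does not dispose of it, because these t-tests are the only planned between-arm comparison of POSAS, and Section 9.6 sizes the trial for such a comparison.

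Four stronger readings are tempting but not supported:

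- *A missed 6-month visit throws away the 1-month score.* The t-tests do not do this; the score still enters the 1-month test. Only the exclusion rule in Section 9.1 could remove it, and discontinuation for missed visits is permitted, not automatic.
- *The bias favours endoscopic release.* Its sign depends on who skips, and the documents do not settle that.
- *The hypothesis is really about the mature scar.* Section 9.3 states it for all three visits alike.
- *The model raises power from 83% to 92% (ρ = 0.5) or 89% (ρ = 0.7).* Those figures belong to the average of the 1-month and 6-month differences, with SD 8 × √((1 + ρ)/2). The plan does not define that contrast, and reporting a difference at each visit does not deliver it.

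**Conclusion.** The concern holds in a limited form. Section 9.5 cannot use a patient's earlier POSAS scores in the 6-month comparison, so that comparison is open to bias whenever attendance depends on the earlier scar in a way that shifts the arms unequally. Under the stated assumptions the bias runs from about −1.6 to +1.9 points. That is up to about a fifth of the 10-point target (1.9/10 = 0.19) and 0.6 of the standard error with complete data (8 × √(2/12) = 3.27; 1.9/3.27 = 0.58). It is about zero if missingness is random or the same within each arm.

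The missing rate, correlation and selection mechanism are all assumptions. The case for change rests on protection against bias; the precision gain is secondary. The exclusion of discontinued subjects in Section 9.1 is the larger threat to the same data and has to be dealt with together with the tests.

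**What to change.** 1. In Section 9.5, replace the three POSAS t-tests by one repeated-measures model fitted by REML, with arm, visit and arm-by-visit, unstructured covariance across the three visits and Kenward-Roger degrees of freedom. Name compound symmetry as the fallback if the unstructured fit fails. Use every POSAS score obtained, and report the arm difference with its 95% confidence interval at each visit.
2. Amend Section 9.1 so that patients who miss visits, or are discontinued after surgery, keep their observed POSAS scores in the analysis. State that a missed visit alone does not remove a patient from the per protocol population. Reconcile this with Section 7.1, with the definition of the full analysis population, and with the use of all available observations in Section 9.
3. Claim power for an averaged 1-month and 6-month difference only if that contrast is prespecified.

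Cost: short changes to two sections and standard software, with no new data and no change to 12 per arm. The model imputes nothing, so it is consistent with Section 9. The downsides are slightly more modelling for 24 patients, and that bias is removed only if attendance depends on observed scores.

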### 9.3 HYPOTHESIS AND METHODS OF ANALYSIS

We hypothesize that patients treated with the retrograde endoscopic approach will have improved scarring compared to patients treated with the open approach, based on POSAS scores obtained at 1 week, 1 month, and 6 months post-operatively. We also hypothesize that the patients in the endoscopic treatment arm will have a faster recovery (return to work sooner with fewer days of occupational therapy), have higher overall satisfaction (scale 1 to 10) and use less pain medication. We anticipate that the two treatments will not differ significantly in complication or recurrence rate.

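### Days to return to work is a time to an event but is analysed by mean and t-test, with no rule for subjects not yet back at work

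*Combined protocol and SAP*

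**What the plan says.** Return to work is a secondary outcome (8.1.2, 9.2.2). With occupational therapy it carries the recovery hypothesis in 9.3, which expects a "faster recovery (return to work sooner with fewer days of occupational therapy") in the endoscopic arm.

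The analysis rules are spread over several sections:

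- **9.3.2:** "days to return to work, days of occupational therapy, complication rate, and recurrence rate will be analyzed using descriptive statistics", listed as n, mean, SD, median, minimum, maximum and skewness.
- **9.5 (exploratory):** "Differences in pain medication use, days before return to work, duration of OT, operative time" and other outcomes "will be tested for significance using 2-sample t-tests".
- **9:** "no imputation of missing data will be performed", and "Descriptive summaries will be based on all observations available within each of the relevant analysis populations".
- **9.1:** "Subjects that have been discontinued will be excluded from data analysis".
- **7.1:** one ground for discontinuation is "Subject does not complete scheduled follow-up visits per protocol".

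Section 6.1.3 collects return to work and therapy duration at 1 week, 1 month and 6 months. Follow-up ends at 6 months (4.3). No section gives a start for the clock, a code for a subject not yet returned, a censoring rule, or a rule for subjects who were not working before surgery. Eligibility (5.3, 5.4) does not require a job, and 6.1.1 does not name work status among the baseline data.

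**The concern.** A day count exists only once the subject has gone back to work. Before that, all that is known is that the time exceeds the follow-up so far. A mean and a t-test cannot use that information. The subjects affected are those known to be slower than everyone who had returned by the same point.

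This does not need anyone to be off work at 6 months. A subject not working at 1 month who then misses the 6-month visit is known only to have taken more than a month. Under 7.1 that subject may be discontinued, and under 9.1 is then excluded. Section 5.1 also allows a withdrawn subject to be replaced, so a slow recovery may be exchanged for a new subject.

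A blank value is ambiguous too: not employed, not yet returned, or not recorded. Therapy still running at the last visit raises the same difficulty for therapy duration. With 12 subjects per arm, one or two such cases can move an arm mean substantially.

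**Working it through.** **The plan's own figure.** The only computed figure is 12 per arm in 9.6, for POSAS (difference 10, SD 8, two-sided 5%, power 80%). The normal approximation gives 2 × (1.960 + 0.842)² × 8² / 10² = 10.05, rounded up to 11. The noncentral t gives 11.09, rounded up to 12, with power 83.3% at 12. The figure reproduces, but it says nothing about return to work.

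**Effect on one arm's mean.** Everything from here on is assumption, because the documents give no return-to-work mean, SD or non-return rate. Let *m* be the mean among returners and *k* the number of 12 not back at 180 days (6 months taken as 180 days). The mean of available values is *m* whatever *k* is. The mean restricted to 180 days is ((12 − k) × m + k × 180) / 12. For m = 14 and k = 1 it is (154 + 180) / 12 = 27.8.

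| Mean of available values | k = 0 | k = 1 | k = 2 | k = 3 |
|---|---|---|---|---|
| 14 | 14.0 | 27.8 | 41.7 | 55.5 |
| 28 | 28.0 | 40.7 | 53.3 | 66.0 |
| 42 | 42.0 | 53.5 | 65.0 | 76.5 |

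**Effect on the difference between arms**, from the same formula:

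- Returners average 28 days in both arms, with 0 endoscopic and 2 open not returned. The available-value difference is 0; the restricted difference is 53.3 − 28.0 = 25.3 days.
- Returners average 28 days in both arms, with 2 not returned in each. Both differences are 0, although each arm mean is 25.3 days too short.
- Returners average 14 and 28 days, with 2 not returned in each arm. The available-value difference is 14 days and the restricted difference 14 × 10/12 = 11.7 days, in the same direction.
- None not returned: the two differences are identical.

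**Choice of test.** A simulation used 2,500 trials per setting, 12 per arm, log-normal times with log SD 0.7, medians of 14 and 28 days, and non-returners censored at 180 days:

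| Expected not returned (endoscopic, open) | t-test on returners | Log-rank |
|---|---|---|
| 0/12, 0/12 | 53.0% | 59.6% |
| 0/12, 2/12 | 52.9% | 81.9% |
| 2/12, 2/12 | 47.0% | 20.0% |

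The ranking of the tests turns on how non-return splits between the arms, which the documents do not inform.

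**The case against.** Several points on the other side stand.

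- **A reader might infer that the plan states that non-returners are dropped.** It does not. The available-observations sentence in section 9 speaks of descriptive summaries, not of the tests in 9.5. Staff could enter days elapsed at the last visit, which would keep the subject in with a value that is too short. What happens depends on a rule the plan does not give. Neither reading handles the censored time correctly, so the point survives.
- **A reader might infer that the comparison will be hidden or reversed.** That needs non-return or loss to differ by arm, and nothing in the documents says it will, or that anyone will still be off work at 6 months.
- **A reader might infer that a log-rank test gains power.** The last table shows that it can lose power.
- **The contrast of 14.0 with 27.8 is not what a Kaplan-Meier analysis would report.** With 11 of 12 returned, the available-case median is the 6th return time. The Kaplan-Meier curve also reaches 6/12 = 0.5 at the 6th return, so the medians agree. Section 9.3.2 already plans the median and n. The mean, SD and t-test remain affected, and n alone does not show why a value is missing.
- **Subjects without a job are not a source of bias in themselves.** They have no return time under any method. What is missing is a record of who they are.

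The outcome is secondary and its test exploratory. That limits the weight of the point but does not remove it, since the descriptive mean in 9.3.2 has the same defect and is a planned summary for the recovery hypothesis.

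**Conclusion.** The point holds in conditional form. Mean, SD and t-test do not suit a time that may be unfinished at last contact, and no other section repairs this. Arm means are too short whenever anyone has not returned. The between-arm difference is biased if non-return or loss to follow-up differs by arm. There is no bias if everyone is seen to return.

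The size is unknown. On the assumed inputs above, one non-returner among 12 hides 11.5 to 13.8 days of an arm's mean restricted to 180 days (53.5 − 42.0 and 27.8 − 14.0). Those figures rest on assumed returner means and on 180 days for 6 months. They illustrate the mechanism and do not predict this trial's result. The case for change is that the method fits the outcome, not that it gains power. The primary POSAS result is unaffected.

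**What to change.** - **9.3.2 and 9.5:** analyse return to work from the day of surgery, among subjects working before surgery. Censor those not yet returned at last contact. Report the Kaplan-Meier curve and median and the number not returned per arm, and replace the t-test with a permutation log-rank test. Censoring is not imputation, so the rule in section 9 can stand.
- **9.1:** amend so that discontinued subjects contribute censored time to this outcome. Without this, the changes to 9.3.2 and 9.5 would not reach them.
- **6.1.1:** record work status at baseline, and report the number not working per arm.
- **Occupational therapy:** count duration from the start of therapy, give zero to subjects with none, and treat therapy still ongoing at last contact as censored.

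The cost is SAP wording and one baseline question, with no added visit or subject. The downsides are a smaller group for this outcome, a median in place of a mean, and possibly lower power if non-return is similar in both arms.

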### 8.1.2 SECONDARY OUTCOME MEASURES

Secondary outcome measures include pain medication use, overall patient satisfaction (score 1 to 10), days to return to work, and duration of post-operative occupational therapy as well as complication and recurrence rates after endoscopic versus open surgical treatment. Complications will include injury to tendons, nerves, and digital vessels noted during or after surgical treatment, as well as surgical site dehiscence and surgical site infections requiring antibiotics. Recurrence will be defined as triggering, confirmed on physical exam by treating physician, at any time point post-operatively.

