#### 9.2.2 SECONDARY OUTCOME MEASURES

Secondary outcome measures include pain medication use, overall patient satisfaction (score 1 to 10), days to return to work, and duration of post-operative occupational therapy as well as complication and recurrence rates after endoscopic versus open surgical treatment. Complications will include injury to tendons, nerves, and digital vessels noted during or after surgical treatment, as well as surgical site dehiscence and surgical site infections requiring antibiotics. Recurrence will be defined as triggering, confirmed on physical exam by treating physician, at any time point post-operatively.

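### Complications and recurrence are event outcomes, yet the plan summarises them by mean, SD, median and skewness with no interval and compares them by a t-test that gives no result when neither arm has an event

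*Combined protocol and SAP*

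**What the plan says.** Section 8.1.2 defines the first outcome by a list of events: "Complications will include injury to tendons, nerves, and digital vessels noted during or after surgical treatment", together with wound dehiscence and infections treated with antibiotics. Section 9.2.2 defines the second: "Recurrence will be defined as triggering, confirmed on physical exam by treating physician, at any time point post-operatively". Each patient either has such an event or does not.

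Section 9.3.2 places both in one list with days, scores and medication use, and ends: "complication rate, and recurrence rate will be analyzed using descriptive statistics, including n, mean, standard deviation, median, minimum, maximum, and skewness". Section 9.5 then lists "operative time, overall satisfaction, complication and recurrence rates between patients treated with endoscopic versus open surgical release" among the outcomes that "of the A1 pulley will be tested for significance using 2-sample t-tests".

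Neither section gives a count with percentage, a risk difference, an exact test or a confidence interval for these two outcomes. Section 9 describes the whole analysis as descriptive: "Due to the descriptive nature of all analyses, no imputation of missing data will be performed".

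**The concern.** Summaries and tests meant for continuous data have been applied to yes/no outcomes that may be rare. Two things follow.

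- The prescribed comparison can come back empty. With no event in either arm there is no variance, and the t-test has no value.
- The prescribed summary does not show precision. An arm with no events would be reported as mean 0, SD 0, which looks exact although 12 patients say little about a rare event.

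Because the plan calls its analyses descriptive, the summary is the main thing the trial will report on these two named secondary outcomes. Section 9.3 also expects no significant difference between the arms in either of them. A blank or non-significant test beside a mean and SD of zero could be read as confirming that, with nothing printed to show how large a difference remains possible.

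**Working it through.** **Inputs.** 12 patients per arm (Sections 5.1 and 9.6); two-sided 5% level (Section 9.6). No event rate is given for either outcome, so the rates below are assumptions, taken as equal in the two arms unless stated.

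**The plan's own figure.** For POSAS, difference 10 and SD 8, the normal formula gives n = 2 × (1.960 + 0.842)² × 8²/10² = 10.05, so 11 per arm. The t-based calculation gives 11.09, rounded up to 12, with 83.3% power at 12. The stated 12 per arm is reproduced. It has no bearing on complications or recurrence, for which the plan gives no power or precision.

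**The t-test with no events.** Code each patient 0/1. At 0/12 v 0/12 both means and both variances are 0, so t = 0/0. Student's and Welch's versions both return no value.

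**How often.** P(no event in 24) = (1 − p)^24. P(at least one arm with no event) = 1 − [1 − (1 − p)^12]².

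| True rate p | No event in 24 (t undefined) | At least one arm with no event (SD 0, skewness undefined) |
|---|---|---|
| 2% | 62% | 95% |
| 5% | 29% | 79% |
| 10% | 8% | 49% |
| 20% | 0.5% | 13% |

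**What the listed summary shows.**

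- 0/12: mean 0, SD 0, median 0, skewness undefined. Mean ± t × SD/√n gives 0 to 0. Clopper-Pearson gives 0 to 1 − 0.025^(1/12) = 26.5%.
- 1/12: mean 0.083, SD 0.289, median 0. The same formula gives 0.083 ± 2.201 × 0.289/√12 = 0.083 ± 0.183, that is −10.0% to +26.7%. Clopper-Pearson gives 0.2% to 38.5%.
- The median is 0 for any arm with 0 to 5 events of 12, so it does not separate those results.

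**Risk difference with an interval that is defined at 0 v 0.**

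| Result | Miettinen-Nurminen 95% CI | Newcombe 95% CI |
|---|---|---|
| 0/12 v 0/12 | −25.0 to +25.0 points | −24.2 to +24.2 points |
| 1/12 v 0/12 | −17.9 to +36.1 points | −16.9 to +35.4 points |

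**Does the t-test mislead when it is defined?** All 13 × 13 = 169 possible tables were enumerated, with undefined results counted as non-significant.

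- Type I error of the t-test: 0.2% at a 5% rate, 1.5% at 10%, 4.9% at 30%. It is not inflated.
- The pooled t-test and Barnard's test reach the same verdict on 165 of 169 tables. They differ only at 3 v 8, 4 v 9 and their mirror images.
- The t-test and Fisher's test disagree in 0.2% of trials at 5% v 5%, 1.2% at 10% v 10% and 3.9% at 5% v 15%. One such table is 4/12 v 0/12: t-test p = 0.028, Fisher p = 0.093.

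**Does another section repair this?** Section 9.3.3 says "All exploratory variables will be summarized with descriptive statistics appropriate to the scale of measurement for each variable", but the only exploratory variable listed in 8.1.3 is operative time; these two outcomes are secondary. The reference to suitable inferential tests at the end of 9.5 concerns optional extra analyses of relationships between outcomes. Section 9.3.4 tabulates adverse events, but does not say by arm and gives no interval.

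**The case against.** The best case for the plan is that little is lost. If patients are coded 0/1, the mean is the event proportion; n and mean then give the count, and any reader can compute an exact interval from it. An undefined t-test at 0 v 0 says the same as a Fisher p-value of 1: no difference was seen. The tests are labelled exploratory, and neither outcome drives the sample size. Many of these events would probably also appear in the adverse event table under 9.3.4. The lack of intervals runs through the whole plan, and the high chances of an empty test depend on assumed rates of a few percent: at 20% the chance is only 0.5%.

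Much of this stands. The verdict rarely changes, error rates are sound, and the count is recoverable under 0/1 coding. But the plan does not state that coding, and the adverse event table is not said to be by arm. The missing interval matters more here than for POSAS, where n, mean and SD yield a usable interval; for a rare event the same three numbers give an interval that collapses to a point or runs below zero. A method known in advance to fail on a plausible result should not be the one written down.

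**Conclusion.** The concern holds, at the level of something that should be changed. For both outcomes the planned comparison is undefined when there are no events (62%, 29% and 8% of trials at assumed true rates of 2%, 5% and 10%, equal in both arms). The planned summary also hides that a true rate of up to 26.5% is compatible with 0/12.

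The limits are equally clear. There is no type I error inflation, the test verdict seldom changes, the primary outcome and sample size are untouched, and the plan makes no formal claim of similarity.

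**What to change.** **Section 9.3.2.** For complications and recurrence, replace mean, SD, median and skewness by the number and percentage of patients with at least one event (n/N, %) in each arm, with a Clopper-Pearson 95% confidence interval.

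**Section 9.5.** Take both outcomes off the t-test list. Report the risk difference, endoscopic minus open, with a score-type 95% interval that is defined at 0 v 0. Name one method in advance: Miettinen-Nurminen or Newcombe would serve.

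**If a p-value is kept,** specify Barnard's exact test. Fisher's test is also valid but costs power: at 5% v 15% the chance of significance falls from 5.2% with the t-test to 1.3% with Fisher.

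**Cost.** A few sentences of SAP text and trivial programming, with no change to data collection, sample size or the primary outcome. The intervals will be wide and the change does not raise power. Check that the chosen software returns an interval at 0 v 0, because at least one standard score routine fails there.
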